10.3 REPORTING ADVERSE EVENTS AND UNANTICIPATED ADVERSE DEVICE EFFECTS

Identification, collection and reporting of adverse event information is the responsibility of the principal investigator. The investigator records the date of the event, its severity, treatment (if any) and the assessed relationship of the event to the study device on the Adverse Event Case Report Form (AE CRF).

Any ocular-related **serious adverse event** (SAE) should be reported to the study sponsor within one working day of learning of the event. Non-ocular-related SAEs should be

reported to the study sponsor within two working days of learning of the event. Email the AE CRF to [REDACTED].

Any **unanticipated adverse device effects (UADE)** must be reported to the following two entities:

1. The study sponsor – Within one working day of the investigator first learning of the event, e-mail the AE CRF to [REDACTED]; and
2. The reviewing IRB – As soon as possible, but no later than 10 working days after the investigator first learns of the event, report per the IRB's instructions.

The sponsor will conduct an evaluation of unanticipated adverse device effects. If the sponsor determines that an unanticipated adverse device effect presents an unreasonable risk to subjects, parts of the investigation presenting risks will be terminated. Termination will occur no later than 5 working days after the sponsor makes such a determination and no later than 15 working days after the sponsor first received notice of the effect.

11 RISK-BENEFIT ANALYSIS

11.1 ANTICIPATED CLINICAL BENEFITS

The TearCare™ procedure will be performed with the aim of reducing the signs and symptoms of dry eye. The goal of the procedure is to provide a safe, reproducible, and effective treatment for dry eye disease, a disease for which there is an unmet need for effective therapies.

11.2 ANTICIPATED ADVERSE DEVICE EFFECTS

Anticipated adverse effects associated with the TearCare System have been described above in Section 10.2.

11.3 RESIDUAL RISKS ASSOCIATED WITH THE TEST DEVICE, AS IDENTIFIED IN THE RISK ANALYSIS REPORT

Sight Sciences believes that there are no Intolerable residual risks from this non-invasive, controlled heat treatment device that can be easily and quickly removed by the subject or by the supervising ophthalmologist, in the event of a complication during a TearCare treatment session.

11.4 RISKS ASSOCIATED WITH PARTICIPATION IN THE CLINICAL INVESTIGATION

All anticipated study risks are listed in Section 10.2.

11.5 POSSIBLE INTERACTIONS WITH CONCOMITANT MEDICAL TREATMENTS

It is anticipated that there will be no interactions with concomitant medical treatments.

11.6 STEPS THAT WILL BE TAKEN TO CONTROL OR MITIGATE THE RISKS

The major risks to the subjects and the steps taken to control or mitigate them are described below:

1. Overheating of the eyelids: All TearCare treatments will be done in the investigator's office under direct supervision of the investigator. The device delivers heat to the eyelids at a temperature ranging from 41-45°C. This temperature range was selected because it is both safe for eyelid heating and effective for melting obstructions in the meibomian glands.^{24,25,26,27} The user can adjust the temperature up or down to a level that is comfortable, and may also shut off the System at any time if it is too uncomfortable or painful. In addition, the TearCare System continuously monitors and regulates the temperature at the tissue-contacting surface of the iLid devices and has been designed to not exceed the maximum allowable temperature.
2. Corneal abrasion: If the iLid devices are not positioned properly or come loose during the treatment, there is the potential for a corneal abrasion. To mitigate this, the supervising physician will apply the strips to the subject and will monitor their position during the treatment to ensure they remain in place and secure.

In addition, there is the possibility of corneal abrasion or abrasion of the eyelid surface during expression of the meibomian glands. To reduce the chance of abrasion, the forceps have been designed with smooth surfaces (i.e. no rough edges) and only trained users will perform expression.

²⁴ Lane SS, DuBiner H, Epstein RJ, et al. A New System, the LipiFlow, for the Treatment of Meibomian Gland Dysfunction. *Cornea*. 2012; 31 : 396-404

²⁵ Blackie CA, Solomon JD, Greiner JV, Holmes M, Korb DR. Inner Eyelid Surface Temperature as a Function of Warm Compress Methodology. *Optom Vis Sci* 2008;85:675-683.

²⁶ Moritz AR, Henriques FC. Studies of thermal injury: the relative importance of time and surface temperature in the causation of cutaneous burns. *Am J Pathol* 1947;23:695-720.

²⁷ Medical electrical equipment Part 1: General requirements for basic safety and essential performance (IEC 60601-1).

3. Worsening of dry eye symptoms: It is possible that subjects will experience a worsening of dry eye symptoms during the study. Subjects will undergo a complete eye exam at each visit and if any untoward or worsening signs of ocular surface disease are observed, they will be treated appropriately.

In addition to the above, the following mitigation steps have also been taken to reduce the risks in this study:

- The device has been tested to demonstrate that it meets performance and safety specifications, as described in Section 5.1.
- Instructions for Use are provided with each device.
- The clinician using the device will be trained in how to safely and correctly apply and remove the iLid devices, and operate the TearCare System.

12 STATISTICAL CONSIDERATIONS

12.1 HYPOTHESIS

This exploratory study is not a hypothesis-driven study.

12.2 SAMPLE SIZE CALCULATION

Given that this is not a hypothesis-driven study, no sample size was calculated for the study. A sample size of up to 30 subjects was chosen for the study as a reasonable number of subjects for this exploratory study to evaluate of the safety and effectiveness of the TearCare System.

12.3 PASS/FAIL CRITERIA

No pass/fail criteria are defined for the study.

12.4 EVALUABILITY

All subjects on whom the TearCare device is attempted will be considered evaluable for the safety analysis. All eyes that have at least one follow-up visit and have no major protocol deviations will be evaluable for the per protocol analysis.

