6 STUDY ENDPOINTS

6.1 EFFECTIVENESS ENDPOINTS

The following endpoints will be assessed:

- **Primary effectiveness endpoint**
 - Mean Change from baseline in Tear Break-Up Time (TBUT)
- **Secondary effectiveness endpoints**
 - Mean Change from baseline in OSDI score²²
 - Mean Change from baseline in the total Meibomian Gland Secretion Score²³

²² Schiffman RM, Christianson MD, Jacobsen G, Hirsch JD, Reis BL. Reliability and validity of the Ocular Surface Disease Index. Arch Ophthalmol 2000;118: 615-621.

²³ Bron AJ, Benjamin L, Snibson GR. Meibomian gland disease. Classification and grading of lid changes. Eye 1991;5: 395-411.

- Mean Change from baseline in corneal staining scores
- Mean Change from baseline in conjunctival staining scores

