7 STUDY DESIGN

This is a prospective, single-arm, exploratory treatment study. This is a post-market study intended to collect clinical data regarding the safety and effectiveness of the TearCare System. To reduce potential bias in the study, study staff performing the endpoint assessments will be independent of the clinician performing the TearCare procedure.

In this study, all subjects will receive the TearCare procedure. The TearCare procedure includes an in-office 15 minute treatment session with the TearCare System immediately (i.e. within 3 minutes) followed by manual expression of the meibomian glands using the Express Forceps. Subjects will receive one in-office TearCare procedure at the baseline visit and will then have follow-up visits at 1 week and 1 month.

This study will be conducted at 2-3 sites in the United States.

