9 STUDY PROCEDURES

9.1 STUDY SCHEDULE

The Study Schedule is shown below in Table 2.

Table 2: Study Visit Schedule

Visit (Visit Window)	Baseline (Day 0)	Wk 1 (Day 5-9)	1 Mo (Day 21 – 35)
Informed Consent	X		
Demographics, Ocular & Medical History	X		
Medication use	X	X	X
OSDI*	X	X	X
Best Spectacle corrected visual acuity (Snellen)*	X	X	X
Slit Lamp Exam*	X	X	X
Tear Breakup Time*	X	X	X
Corneal Staining*	X	X	X
Conjunctival Staining*	X	X	X
Meibomian Gland Secretion Scoring*	X	X	X
TearCare Treatment	X		
AE Assessment*	X	X	X
Lubricant Drops Log			X

* Endpoint assessment should be performed by an independent study staff who does not perform the TearCare procedure on study subjects.

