12.5 ANALYSIS POPULATIONS

The per-protocol analysis population includes all subjects who have at least one post-treatment visit and have no major protocol deviations, including specifically no use of dry-eye medications (Xiidra, Restasis). The primary and secondary endpoint analyses will be carried out on the per-protocol population. The primary analysis population will be per-protocol.

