16 DEVICE FAILURES AND MALFUNCTIONS

All device failures or malfunctions should be recorded on the Device Deficiency Form and reported to Sight Sciences Customer Service [REDACTED]

If the TearCare procedure cannot be completed due to a product failure or malfunction, the procedure may be rescheduled for a different day. Every effort should be made to reschedule the procedure within the next 7 calendar days of the Baseline visit.

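### Must the plan name a visit for the primary TBUT change and tighten its follow-up rule, given sections 6.1, 12.4, 12.5 and 16?

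*Combined protocol and SAP*

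**What the plan says.** Section 6.1 gives the primary endpoint as "Mean Change from baseline in Tear Break-Up Time (TBUT", with no visit. The synopsis gives only the name of the measure. Table 2 (section 9.1) schedules TBUT at Baseline, Week 1 (Day 5-9) and 1 Month (Day 21-35), with Baseline as Day 0.

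Two sections decide whose data count. Section 12.4: "All eyes that have at least one follow-up visit and have no major protocol deviations will be evaluable for the per protocol analysis". Section 12.5: "The per-protocol analysis population includes all subjects who have at least one post-treatment visit", again subject to no major deviations, and then "The primary and secondary endpoint analyses will be carried out on the per-protocol population". The first speaks of eyes and follow-up visits, the second of subjects and post-treatment visits.

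Section 7 sets the normal order: "Subjects will receive one in-office TearCare procedure at the baseline visit and will then have follow-up visits at 1 week and 1 month". Section 16 covers a procedure that a product failure prevents from being completed: "the procedure may be rescheduled for a different day", and "Every effort should be made to reschedule the procedure within the next 7 calendar days of the Baseline visit". It does not say whether the visit windows move with the procedure.

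Sections 12.1, 12.3 and 12.7 state that there is no hypothesis, no pass/fail criterion and no analysis beyond basic description. Section 12.6 promises an accounting of subjects at each visit, with reasons for dropout where known.

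**The concern.** An endpoint labelled primary but measured at two visits leaves open which value is the headline. If the choice were made after the data were seen, the better visit could be reported, and section 12.9 would not catch it because no visit was planned.

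One visit is enough to enter the per-protocol set. A subject seen only at Week 1 therefore belongs to it without a 1 Month value, and no handling is stated.

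Windows counted from Baseline, combined with a movable procedure, allow an in-window Week 1 visit before treatment. Read literally, 12.4 might accept such a visit and 12.5 would not. A pre-treatment value could then sit in the Week 1 column as a change after treatment. The difference between eyes and subjects adds doubt about the unit.

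**Working it through.** The plan contains no sample size, power or error-rate calculation, so there is no figure to reproduce. The checks are date arithmetic and the size of each effect.

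**1. Choice of visit.** Inputs: SD of TBUT change 2.6 s and mean change 11.7 s (pilot, section 5.2, treated group at 1 month); n = 30 (the maximum, section 9.2); correlation r between visits, assumed 0.3 to 0.8. If both visits have the same true mean, reporting the better one adds (SD/√n) × √((1 − r)/π) on average.

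- SD/√n = 2.6/√30 = 0.475 s.
- r = 0.3: 0.475 × √(0.7/π) = 0.224 s.
- r = 0.5: 0.475 × √(0.5/π) = 0.189 s.
- r = 0.8: 0.475 × √(0.2/π) = 0.120 s.

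Against 11.7 s this is 0.120/11.7 = 1.0% to 0.224/11.7 = 1.9%. Pilot Table 1 is headed by eyes as well as subjects, so the unit behind the SD is uncertain.

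**2. Subjects seen only at Week 1.** The 1 Month mean differs between completers and last available value by k × G/n, where k such subjects fall short of the rest by G. If they responded like the others, G = 0 and the shift is 0. If they did not respond, take G = 11.7 − (−0.3) = 12.0 s, the pilot contrast: 12.0/30 = 0.40 s for each subject. Section 12.6 would show them as absent at 1 Month, and observed data by visit is the ordinary reading of basic descriptive statistics.

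**3. Rescheduling.** With the procedure on Day d, an in-window Week 1 visit falls 5 − d to 9 − d days after it, and a 1 Month visit 21 − d to 35 − d days after it.

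| Procedure day | Week 1, days after procedure | 1 Month, days after procedure |
|---|---|---|
| 0 | 5 to 9 | 21 to 35 |
| 5 | 0 to 4 | 16 to 30 |
| 6 | −1 to 3 | 15 to 29 |
| 7 | −2 to 2 | 14 to 28 |

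For procedure Days 1 to 7 and visit Days 5 to 9 there are 7 × 5 = 35 combinations. In three of them the visit comes first (procedure Day 6 with visit Day 5; procedure Day 7 with visit Day 5 or 6). This counts what is possible, not how likely it is.

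If k of 30 subjects had a pre-treatment Week 1 value, the mean would fall by k × 12.0/30: 0.40 s for one and 1.20 s for three. These figures are illustrative. The contrast is against daily warm compresses, not no treatment; the pilot heated for 12 minutes against 15 here; and the documents give no Week 1 result.

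**4. What follow-up means.** Section 7 places follow-up after the procedure. Section 9.6 bars the clinician who has already treated the subject from doing the follow-up exams. Table 2 puts the treatment in the Day 0 column, so Day 0 is both the baseline day and the treatment day. On this usage, follow-up in 12.4 and post-treatment in 12.5 are synonyms. An exam held before treatment would also depart from section 7 and be documented as a deviation under section 15. Section 16 requires every device failure to be recorded, so the subjects concerned can be identified.

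**5. Unit.** When both eyes of every subject contribute, the mean over 60 eyes equals the mean of 30 subject averages. Only the stated n differs.

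**The case for a change.** The best argument for a change is that naming a visit costs one phrase. The pilot named one (4 weeks), and its treated mean TBUT was 14.8 s at 4 weeks and 7.9 s at 6 months, so timing matters. Section 14.2 allows publication for marketing as well as science, and calling a study exploratory does not excuse leaving its primary endpoint without a time point. The 7-day limit in section 16 is also only best effort: with the procedure on Day 10 or later, the whole Week 1 window precedes it, and the 14-day minimum before a 1 Month visit no longer holds.

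The facts stand. No visit is named, and Table 2, section 7 and section 16 do not say from which day visits count after a rescheduled procedure. The sponsor must reconcile those passages if the case arises; this review takes no position on the timing. The consequence does not follow. There are only two visits, within about a month of each other, and a descriptive report shows both. The pilot's contrast between 4 weeks and 6 months says little about Week 1 against 1 Month. No test, interval or decision turns on the choice.

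**Conclusion.** No change to the plan is needed. The missing visit, the missing rule for Week 1-only subjects and the mixed unit are gaps that an analyst fills sensibly: observed changes at Week 1 and 1 Month, with numbers of subjects and eyes at each. The difference in terms between 12.4 and 12.5 is a slip of wording that the rest of the protocol resolves.

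The core gap is worth about 0.12 to 0.22 s, on the pilot SD, n = 30, equal true means and assumed correlations of 0.3 to 0.8. The larger figures, 0.40 s per affected subject, rest on a borrowed contrast and on events whose frequency the documents do not give; if nobody is rescheduled late or seen only at Week 1, they are zero. The conclusion assumes that both visits are reported and that exams before treatment are not counted as follow-up. It would not carry over to a study with a test or success criterion tied to the primary endpoint.

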At 1 month follow-up, TearCare subjects demonstrated an improvement from baseline in mean (\pm SD) TBUT of 11.7 ± 2.6 seconds compared with an average worsening of -0.3 ± 1.1 seconds for subjects in the warm compress group ($p<0.0001$). Significantly greater improvements in the change from baseline in meibomian gland scores, as well as corneal and conjunctival staining scores were observed in the TearCare group. Subjects in the TearCare group also showed significantly greater improvement in dry eye symptoms as measured by the three questionnaires.

No adverse events were reported in either group.

Table 1: TearCare System – Pilot Study Results (2017)

	TearCare (n=24 eyes, 12 subjects)			Warm Compress control (n=24 eyes, 12 subjects)		
	Baseline	4 weeks	6 months	Baseline	4 weeks	6 months
Tear Break-up Time (sec) – Mean (SD)	3.1 (0.8)	14.8 (2.6)	7.9 (1.5)	3.3 (1.0)	3.1 (0.8)	3.0 (1.0)
Dry Eye Symptom Questionnaires						
Total OSDI Score (0 to 100)	41.0 (18.4)	15.7 (12.2)	30.3 (15.1)	33.0 (19.9)	24.6 (15.2)	30.3 (15.1)
Total SPEED Score (0 to 28)	15.7 (5.2)	7.8 (3.5)	8.2 (6.0)	14.4 (3.8)	12.6 (3.3)	12.2 (4.0)
Total SANDE Score	64.9 (25.9)	40.2 (18.8)	45.9 (30.5)	55.9 (31.5)	57.5 (25.7)	62.1 (21.8)
Meibomian Gland Assessment						
Total Meibomian Gland Score (0 to 45)	6.3 (3.6)	41.0 (2.1)	31.5 (5.5)	9.0 (4.3)	8.2 (4.0)	9.4 (3.5)
# Glands Secreting Any Liquid (0 to 15)	0.8 (0.9)	14.6 (0.8)	11.5 (2.4)	1.3 (1.7)	1.3 (1.6)	1.7 (1.5)
# Glands Yield Clear Liquid (0 to 15)	0.0 (0.0)	11.4 (1.6)	5.4 (3.0)	0.3 (0.7)	0.0 (0.0)	0.1 (0.4)
Corneal Staining Score (0 to 15)	3.5 (1.8)	0.2 (0.4)	3.2 (2.6)	3.4 (2.9)	3.2 (2.6)	3.2 (2.8)
Conjunctival Staining Score (0 to 15)	3.7 (2.5)	0.1 (0.3)	0.3 (0.7)	3.0 (3.4)	4.1 (3.5)	3.2 (3.1)

Conclusions

The TearCare Group consistently showed a significant improvement between the baseline and 4 weeks follow-up for all outcome measures, whereas the Warm Compress group did not. For all outcome measures, the TearCare Group's mean change between baseline and 4 weeks follow-up was better than the Warm Compress group. These results were maintained out to 6 months.

This pilot study provided preliminary evidence of the safety and effectiveness of the TearCare device in relieving the signs and symptoms of dry eye.

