8 STUDY SELECTION CRITERIA

8.1 INCLUSION CRITERIA

For inclusion in this study, subjects must meet all of the following criteria:

1. At least 22 years of age
2. Reports dry eye symptoms within the past 3 months
3. Reports having to use artificial tears or lubricants regularly over the past month to relieve dry eye symptoms.
4. OSDI Score of ≥ 23
5. TBUT of ≤ 7 seconds in both eyes
6. Meibomian gland obstruction in both eyes based on a total Meibomian Gland Secretion Score ≤ 15 in each eye.

7. At least 15 glands in each lower eyelid should be expressible, with a sterile cotton swab, at the slit lamp.
8. Best spectacle corrected visual acuity of 20/100 or better in both eyes.
9. Willing and able to comply with the study procedures and follow-up
10. Willing and able to provide informed consent
11. English-speaking

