8.2 EXCLUSION CRITERIA

A subject who meets any of the criteria listed below (in either eye) will be excluded from the study:

1. Any active, clinically significant ocular or peri-ocular infection or inflammation
2. Recurrent clinically significant eye inflammation, other than dry eye, within 3 months prior to enrollment
3. History of eyelid, conjunctiva or corneal surgery (including refractive surgery) within the past year. In addition, subjects with any history of the following are excluded: chalazion surgery, surgery on the tarsal conjunctiva, radial keratotomy (RK), complicated blepharoplasty, lid reconstruction, or significant complications post-refractive surgery.
4. Any office-based dry eye treatment (e.g. IPL, thermal pulsation [Lipiflow], etc.) within 12 months prior to enrollment. In addition Blephex or debridement within 3 months prior to enrollment is an exclusion.
5. Meibomian gland expression within 6 months prior to enrollment. In addition, any history of meibomian gland probing is an exclusion.
6. In the clinical judgement of the investigator, meibomian glands have significant capping, atrophy, or are unable to be expressed, digitally or with a sterile cotton swab.
7. Contact lens use within the past 2 weeks (Subjects must refrain from wearing contact lenses for the duration of the study.)
8. Use of TrueTear device within the past 2 weeks (Subjects must refrain from using the TrueTear device for the duration of the study.)
9. History of Ocular Herpes Simplex or Ocular Herpes Zoster
10. Clinically significant ocular surface abnormalities that may affect tear film distribution or treatment (e.g. pterygium, anterior membrane dystrophy, etc.)
11. Clinically significant eyelid abnormalities in either eye (e.g. entropion/ectropion, blepharospasm, aponeurotic ptosis, lagophthalmos, notching of lid margin, distichiasis, trichiasis)
12. Clinically significant anterior blepharitis. In addition, collarettes or flakes of more than one quarter of the eyelid are excluded.
13. Clinically significant dermatologic or cutaneous disease of the eyelid or periocular area

14. Ocular trauma within 3 months prior to enrollment
15. Any active, clinically significant allergic, vernal, or giant papillary conjunctivitis
16. Known history of diminished or abnormal facial, periocular, ocular or corneal sensation

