9.5.4 MANAGEMENT OF DRY EYE SYMPTOMS DURING FOLLOW-UP

During follow-up, if subjects require relief of their dry eye symptoms, they should only use Refresh® Plus drops. Other types of over-the-counter lubricants should not be used. Subjects should record their daily use of lubricants on the Lubricant Drop log.

Subjects **should not use** any other method of relieving dry eye symptoms, including any of the following:

- Warm compress
- Restasis or Xiidra
- Other dry eye treatments (e.g. Lipiflow, TrueTear, iLux, punctal plugs, etc.)
- Lubricants other than Refresh Plus

NOTE: If a subject had a punctal plug at the baseline visit and it falls out during the study, it should be replaced.

Review these instructions with subjects at the end of the Baseline visit and provide them with the Lubricant Drop log. They should complete the log each day and bring it back to the clinic at the 1 month follow-up visit.

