20 APPENDIX A – METHODS FOR EXAMS, TESTS AND QUESTIONNAIRES

20.1 OSDI

The subject should complete the OSDI at the beginning of each visit before conducting other clinical testing. Provide a paper copy of the questionnaires and a blue or black ink pen to the subject. Review the instructions for the questionnaire with the subject and answer any questions they have about how to complete them. Then allow the subject to complete the questionnaires on their own (i.e. self-administered). The study staff should strictly restrain from interpreting the questions, using suggestive comments and writing on the questionnaires.

Study staff should review the completed questionnaire before the subject leaves the office to check for missing or multiple answers on a given question. If these are found, please point this out to the subject and allow them to revise their response(s) to the specific question(s). Please confirm initials and date of the subject on the last page of the questionnaire. Do not allow the subject to take the questionnaires home.

The OSDI has 12 questions. Based on the answers provided by the subject, study staff calculate the overall OSDI Total score (from 0-100) and scores for the three subscales according to the OSDI instructions. Based on the recommended cutoffs for OSDI Total score, the severity of the subject's dry eye symptoms will be categorized as follows:

- Normal – 0-12
- Mild – 13-22
- Moderate – 23-32
- Severe – 33 or higher

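### Do sections 12.4 (eyes) and 12.5 (subjects) define two different per-protocol sets, and does the lack of a two-eye rule need a change to the plan?

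*Combined protocol and SAP*

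**What the plan says.** Two neighbouring sections of the combined protocol and SAP describe the per-protocol set.

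- 12.4 Evaluability uses subjects for safety and then eyes for per-protocol: "All eyes that have at least one follow-up visit and have no major protocol deviations will be evaluable for the per protocol analysis".
- Section 12.5, on the populations for analysis, uses subjects: "The per-protocol analysis population includes all subjects who have at least one post-treatment visit and have no major protocol deviations". It names one major deviation, use of Xiidra or Restasis. It adds that "The primary and secondary endpoint analyses will be carried out on the per-protocol population".

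Eligibility is set on both eyes together. Section 8.1 asks for "TBUT of ≤ 7 seconds in both eyes" and sets the gland-score limit for each eye. Section 8.2 opens with "A subject who meets any of the criteria listed below (in either eye) will be excluded from the study".

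The endpoints in 6.1 are mean changes from baseline, with no unit stated. In Appendix A, TBUT is the average of three repeat readings (20.4), staining is summed over areas of the ocular surface (Figure 4, in 20.5), and the gland score is totalled over 15 glands per eye (20.7). None of these combines the two eyes. The OSDI is one score per subject (20.1).

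Section 12.1 states no hypothesis, 12.3 sets no pass/fail criteria, and 12.7 limits the analysis to basic descriptive statistics.

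**The concern.** Read literally, the two sections treat a one-eye deviation differently. Section 12.4 keeps the fellow eye in the per-protocol analysis, while 12.5 removes the subject and so both eyes. Neither section refers to the other. The per-protocol population carries the primary endpoint, so the set behind the main TBUT mean would seem to depend on which section the analyst follows, and that choice could be made after the data are seen.

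The missing two-eye rule adds to this. The table for the primary endpoint could show up to 30 subjects or up to 60 eyes, and the SD beside the mean would depend on which. The pilot table in 5.2 gives both counts, 24 eyes and 12 subjects per arm, but it describes an earlier study and does not bind this one.

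**Working it through.** **Inputs.** Up to 30 subjects (9.2), both eyes treated (9.5.3), so up to 60 eyes. From the pilot (5.2), for illustration only: TBUT 3.1 s at baseline and 14.8 s at 4 weeks, a change of 14.8 − 3.1 = 11.7 s, with SD of change 2.6 s. The number *k* of subjects with a major deviation in one eye only is not in the documents; 1 to 3 is assumed.

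**Step 1. Do the sections disagree for the named deviation?** Xiidra or Restasis use, as 12.5 states it, is recorded for the subject. Under 12.5 the subject leaves. Under 12.4 both of that subject's eyes carry the deviation and leave. The set is the same.

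**Step 2. Do the eligibility rules create one-eye cases?** Sections 8.1 and 8.2 make a failure in either eye a failure of the subject, and 9.5.2 treats a subject who does not meet all criteria as a screen failure. These rules point to attribution by subject. They do not leave an eligible fellow eye behind.

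**Step 3. Is any other one-eye deviation identified?** The nearest candidate is the note in 9.5.4: "If a subject had a punctal plug at the baseline visit and it falls out during the study, it should be replaced". A plug not replaced would be a one-eye departure, but no section classes it as a major deviation.

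**Step 4. Does the unit matter when pairs are complete?** With *n* subjects and both eyes measured, the mean of the subject averages is Σ[(L + R)/2]/n = Σ(L + R)/(2n), which is the mean over all 2n eyes. The two means are identical.

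**Step 5. Size if one-eye deviations did occur.** Section 12.4 leaves 60 − k eyes. Section 12.5 leaves 30 − k subjects, or 60 − 2k eyes. Let the k disputed fellow eyes differ from the rest by *d* on average.

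- Eyes pooled: the two means differ by k·d/(60 − k).
- Eyes averaged within subject, with a disputed subject represented by the fellow eye: they differ by k·d/30.

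| k | Eyes, 12.4 | Subjects (eyes), 12.5 | Pooled, d = 2.6 s | Per subject, d = 2.6 s | Pooled, d = 11.7 s | Per subject, d = 11.7 s |
|---|---|---|---|---|---|---|
| 1 | 59 | 29 (58) | 0.04 s | 0.09 s | 0.20 s | 0.39 s |
| 2 | 58 | 28 (56) | 0.09 s | 0.17 s | 0.40 s | 0.78 s |
| 3 | 57 | 27 (54) | 0.14 s | 0.26 s | 0.62 s | 1.17 s |

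The columns for d = 2.6 s need every disputed eye to lie one pilot SD away in the same direction. The columns for d = 11.7 s need every disputed eye to show no change at all. They are extreme illustrations and not bounds, since eyes that worsened would go further.

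**Step 6. OSDI.** An eye-level evaluability rule says nothing about a score that belongs to the subject. Only 12.5 addresses it, and 12.5 puts the secondary endpoints on the subject-defined population. There is no conflict here.

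**The case for a change.** The best case for a change is that 12.4 says outright that an unaffected eye is evaluable, so a reading that requires both an evaluable eye and a per-protocol subject is supplied by the reader. Section 12.5 names one major deviation and leaves the rest open. Gland expression is done eye by eye (9.5.3), so a departure in one eye is possible. Section 12.9, which has departures from the statistical plan noted in the final report, might not catch the choice, because either reading follows one of the two sections. The two-eye gap needs no deviation at all, and one or two sentences would close both.

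Most of this is accurate as a description of the text, and the displayed *n* and SD do depend on the unit. It does not show that a result would be wrong. Section 12.5 is the section that defines analysis populations and assigns endpoints to them. The natural reading is that subjects form the set and their eyes supply the measurements. The reference in 12.4 to all eyes also argues against picking a study eye or a worse eye afterwards. With no hypothesis, interval or success threshold, there is little to gain from choosing late. An SE that treated 60 eyes as independent would be too small if the eyes were positively correlated, but the plan calls for no SE.

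**Conclusion.** No change is needed. The wording of 12.4 and 12.5 differs in unit, and no section states a two-eye rule, but this is a detail that analysts fill sensibly. The sections agree for the one named major deviation. OSDI is settled by 12.5 alone. With complete pairs and no one-eye deviation, the pooled-eye and subject-averaged means are equal.

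If 1 to 3 of 30 subjects did have a one-eye major deviation, a one-SD departure in the fellow eyes would move the TBUT mean by 0.04 to 0.26 s across the two conventions, or 0.4% to 2.2% of the pilot change (0.044/11.7 and 0.26/11.7). That rests on an assumed frequency and on pilot figures. Either reading, applied as written, gives a sound descriptive mean. Giving both eye and subject counts in the tables, as the pilot table did, is ordinary reporting practice and would tell a reader which unit was used.
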